D.1. Design and Randomization: Subjects will be drawn from Fetter Health Care Network (FHCN). It is the sole FQHC center in the 4-county area (8 clinics) and provides ~60% of routine AA healthcare in the 4 county area.¹⁰⁷ A support letter from the FQHC network is included. EMR files indicated they have ~2,619 AAs (21-59 yrs old; mean age=45.3yrs) with sole diagnosis of uncontrolled HTN. We will use the 8 practice sites in a 2 arm RCT design (n=192) with clinic as unit of randomization and patient as unit of analysis. All primary healthcare providers across the 8 clinics have agreed to participate if selected. Each clinic has a minimum of 2 primary providers (at least 1 MD and 1 or more NPs and/or PAs per clinic). Thus, 2 providers per site will be recruited. Each will have 12 of their patients recruited (24 per clinic). Given our ~90% participation rate in previous FQHC studies^{25,108,109} and 93% SMASH participation rate, we anticipate no recruitment problems. The Medical University of South Carolina Family Medicine and Internal Medicine clinic population will be an additional recruitment resource if needed.

D.2. Participants: With consideration of the relevant biological variable of gender, we will recruit 192 AA 21-59 yr old uncontrolled HTNs with equal numbers of males and females that meet the following inclusion/ exclusion criteria: 1) SBP ≥ 140 mmHg on most recent clinic visit over last 12 mos and at BP screening and recruitment visits; 2) MPR < 0.85 over last 3 mos; 3) 24-hour SBP ≥ 130 mmHg (HTN cutoff) to help rule out white coat HTN.^{76,110} SBP used as selection variable since most AA HTNs < 60 have systolic or combination systolic/ diastolic HTN and for most patients, controlling SBP also results in DBP control;^{27,111,112} 4) no other known chronic diseases (e.g., diabetes, chronic kidney disease (GFR < 50 ml/1.73 m²/min), cancer, renal dialysis, heart attack, coronary artery bypass, arterial stent, substance abuse (e.g., > 21 drinks/week), psychiatric illness, Beck Depression Inventory¹¹³⁻¹¹⁵ > 13 , able to speak, hear and understand English; take own BP and meds; 6) owns smart phone with current data plan; 7) primary care MD's assent patient able to participate and 8) no planned pregnancy or vulnerable population (e.g., pregnant or nursing women, prisoners).

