D.3.b. MNA Identification Phase: Subjects will be shown how MedMinder™ works and demonstrate proficiency in loading and activating the device. They will be told their doctors will receive summary reports on their med intake patterns. The tray plugs into a standard 110v outlet, has 28 compartments allowing up to 4 dose times per day for 7 days, and is capable of providing escalating reminder signals (described in D.5.a). **Reminder functions will be disabled for the 1-month screening phase.** The nurse manager (or project manager, [name]) and subject will program the MedMinder for dosing times (example of subject's 24-hr MedMinder activity in Appx. 23). Subject will receive written and oral instructions on MA criteria (i.e., all meds taken within 180 min window centered on prescribed dosing time). SMASH app has auto call feature for TACHL service line for technical issues. Time and date stamped opening and closure of the tray's compartments are relayed via GSM wireless cellular transmitter/receiver to MedMinder™ server for processing. The encrypted data are sent to a HIPPA-compliant server database housed in the TACHL center. The MA formula will be used to calculate MA scores.^{22,23,52,121} (see Appx. 2) **Only subjects with MA score < 0.85 over the 4 week screening and whose subsequent resting and 24-hr SBP evaluations reconfirm uncontrolled HTN will be eligible for enrollment into the RCT.** [name] will randomly assign the 8 sites to either SMASH or

enhanced SC conditions.

D.4. Time Table (Table 2) Based on our SMASH trials, we will recruit 16 subjects/mo beginning mo 4 and finish recruiting by mo 15. We will provide a smart phone and/or service plan for ~40 SMASHers we project might lose phones or service plans during the trial.^{20,21,25,27} Post-trial data collection will finish in mo 34. Post study focus groups and subsequent qualitative analyses will end in mo 43. Table 2 presents a timetable for the study.

Activity	Month
Set-up	Mos 1-3
Recruitment	Mos 4-15
Intervention	Mos 5-22
Follow-up	Mos 16-34
Focus Groups	Mos 35-37
Statistical analyses	Mos 23-28
Prep. and Submission of Effectiveness RCT RO1	Mos 36-42
	Mos 43-48
Month	0 2 4 6 8 10 12 14 16 18 20 22 24 26 28 30 32 34 36 38 40 42 44 46 48
Year	1 2 3 4

D.5. SMASH Protocol:

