D.5.a. Patient Level: Subjects whose practice site is randomly assigned the SMASH condition are termed **SMASHers**. The nurse manager or [name] will confirm with the doctor and patient the med regimen and times meds will be taken daily (example of subject’s 24-hr MedMinder activity in Appx. 23). **SMASHers will have MedMinder’s reminder functions activated.** (Enhanced SC care group will not receive reminders, see D.5.c.) Initially, the designated pill compartment on the tray (28 compartments for up to 4 doses/day for 7 days) emits a bright white blinking light for 30 minutes when it is time to take the meds. If the compartment is not opened, cup removed and emptied within that time, an intermittent chime ensues for 30 minutes. If the cup is not opened, removed, emptied and returned during that time period, the subject receives an automated SMS or voicemail according to his/her preference. They will be provided and instructed on use of the validated Bluetooth-enabled UA-767 Plus BP monitor.¹²² The SMASH app will be installed on their phone that includes audio, text and graphic step-by-step instructions with countdown timers for the 3 readings over the 10 min protocol, and a 1-min refresher training video. BP data are securely received on the phone and sent to the TACHL-housed server. SMASHers will receive written and oral info on adherence criteria: 1) take all meds within 180 min window (90 min before or after dosing times); 2) take BP every 3 days in morning and evening (protocol in Appx. 24). They will correctly load and operate the tray, use the app and BP monitor before leaving the clinic.

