
will have a wealth of data to address important issues not detailed which will guide our future work. For example, we will use triangulation of Morisky MA self-report scale, MPR, pharmacy record information and MedMinder data to develop an effective algorithm for MA measurement.

PROTECTION OF HUMAN SUBJECTS

This Human Subjects Research meets the definition of a clinical trial.

1. Risks to Human Subjects

a. Human Subjects Involvement, Characteristics, and Design

This will be a two-arm RCT design that will assess efficacy of the SMASH mHealth program compared to an enhanced standard care (SC) program. Participants will be drawn from Fetter Health Care Network (FHCN), the sole FQHC center in the 4-county area (Charleston, Dorchester, Colleton and Berkeley counties). The Medical University of South Carolina Family Medicine and Internal Medicine clinics will be available if needed for recruitment of participants. Collectively, this offers a unique opportunity to recruit underserved, at risk patients without extensive screening protocols. We will recruit 192 AAs with uncontrolled HTN (no other comorbidities) and MNA according to the inclusion and exclusion criteria below and the methods described in Section D.2. Participants. The Fetter Health Center Information Technology Department will provide a list of potentially eligible patients to the SMASH project manager, [name]. She will make the initial phone contact with potential subjects. She will inform them about the study and that they will have an equal chance of being randomized to either the enhanced health education (i.e., enhanced standard care [SC]) or SMASH cohort if they are found eligible at the conclusion of the screening period. Following a successful BP screening (SBP ≥ 140 mmHg), a battery of questionnaires are completed and then 24-hour BP monitoring will occur. Likelihood of white coat hypertension in these patients is low.^{30,75,76} We found no case of white coat hypertension in the FQHC feasibility trial involving AAs. If the participant's 24 hour SBP is ≥ 130 mmHg, he/she will proceed to the next phase of screening involving use of the Maya MedMinder for one month with reminder signals deactivated. If MA score $< .85$, they will again complete the baseline clinic BP evaluation and 24-hr BP monitoring to reconfirm uncontrolled SBP HTN.

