The practice sites will have been randomly assigned to SMASH or SC. The MDs and nurse managers at each site will have received an orientation in the SMASH study and refresher on the JNC8 Guidelines for HTN management. **As in our feasibility trials, the project research technicians responsible for conducting all evaluations will remain blinded to the subjects' status for the entire duration of the study and follow-up.** To help prevent contamination, the SMASH and SC subjects will be reminded by phone the night before study evaluations by [name] and again in clinic by the nurse manager, not to discuss their involvement in the trial with the technicians. Subjects will also be instructed not to discuss their treatment regimen with other individuals excepting those in their household. **The SMASH project manager, [name], will not be directly involved with data collection, as she will be a phone contact for SMASH subjects and will not be blinded.** This same approach was successful in the 6-month FQHC feasibility trial.

Primary clinical outcome variables are 1) fraction of subjects reaching JNC8 guidelines for BP control (i.e., resting BP $< 140/90$ mmHg), and 2) fraction of subjects with medication adherence score > 0.90 , as measured by electronic medication tray. Secondary clinical outcome measures include provider adherence to JNC8 guidelines, as measured by timing of medication changes, % reaching 24-hr ambulatory BP control (BP $< 130/80$ mmHg) and changes in subjects' SDT constructs of competence and autonomous motivation. Exploratory outcome variables will include cost effectiveness, other MA indices (i.e., pharmacy record based medication possession ratio [MPR] and self-report [Morisky scale]) and examination of potential moderators (e.g., gender, age, income, etc.) and mediators (e.g., competence, autonomous motivation, perceived disease severity, med side effects, depressive symptoms, sleep quality, etc.) on MA and BP control. We will also explore impact of SMASH program (i.e., increases in MA) upon changes in physical risk factors of TC, LDL, HgA1c and blood glucose. All data will be evaluated on an intent-to-treat basis.

Inclusion Criteria:

1. 21-59 years old; male or female; African American or Black
2. Prescribed medication(s) only for HTN;
3. Medication possession ratio (MPR) $< .85$ for last 3 months;

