4. uncontrolled HTN (SBP ≥ 140 mmHg) based upon last clinic visit within previous 12 months, initial clinic screening and subsequent recruitment evaluation following one month med intake screening with score of $< .85$;

5. 24-hour SBP \geq 130 mmHg on clinic screening and subsequent recruitment evaluation;
6. Ability to speak, hear and understand English;
7. Able to take their own BP and self-administer medications;
8. Owns smart phone with data plan;
9. Primary care provider's assent that patient is able to participate

Exclusion Criteria:

1. No other known chronic disease (e.g., chronic kidney disease (GFR $<$ 50 mL/1.7 m²/min; diabetes (type one or two); renal dialysis ; cancer diagnosis or treatment in past 2 years; prior cv event such as heart attack, congestive heart failure, arterial stent, coronary artery bypass graft ; psychiatric illness
2. Beck Depression Inventory score $>$ 13
3. Ongoing substance abuse (e.g., $>$ 21 drinks/week);
4. Planned pregnancy;
5. Vulnerable populations such as pregnant or nursing women, prisoners, and institutionalized individuals.

Healthcare Team Focus Groups: The 8 primary providers and their nurse managers whose 4 practice sites are randomly selected to deliver SMASH will be eligible to attend a focus group after all patients have completed the final follow-up. All participants will provide written informed consent before taking part in the focus groups and we anticipate that, as before, all healthcare team members will participate. Due to the nature of this sample, a targeted/planned enrollment recruitment table based on gender, race, or ethnicity was not developed.

b. Sources of Materials

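### Candidates are told they have an equal chance of either arm, but clinics are randomised, so once the sites are drawn the statement is untrue for every patient called

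*Combined protocol and SAP*

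**What the plan says.** **What candidates are told.** Protection of Human Subjects, section 1.a, describes the project manager's first phone call. Candidates hear that "they will have an equal chance of being randomized to either the enhanced health education" arm or the SMASH arm, "if they are found eligible at the conclusion of the screening period". The same section says that she is not blinded.

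**How patients are allocated.** Section D.1 sets out a two-arm trial "with clinic as unit of randomization and patient as unit of analysis". Section D.5.a follows this: "Subjects whose practice site is randomly assigned the SMASH condition are termed" SMASHers. Section D.5.c defines the standard care (SC) subjects by site in the same way.

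**When sites are allocated.** Two places bear on this, and neither gives a date.
- Human Subjects 1.a, just after the screening description: "The practice sites will have been randomly assigned to SMASH or SC".
- Section D.3.b, just after the eligibility rule that closes the four-week tray screen: a named team member "will randomly assign the 8 sites to either SMASH or" enhanced SC.

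No section has patients told that their clinic determines their arm.

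**The concern.** The phone statement attributes to the trial a step that it does not contain: a separate even draw for each patient who passes screening. What is drawn is the clinic. Once that draw has been made, a candidate at an SC clinic cannot receive SMASH, and a candidate at a SMASH clinic cannot receive SC.

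What is at stake is the accuracy of what people hear before they take on a demanding screen: a 24-hour blood pressure recording, a month with the monitored tray, and a second 24-hour recording for those still eligible. The caller is unblinded, so after the draw she may be quoting an even chance while knowing the arm. The point does not touch power, type I error or the planned analysis.

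**Working it through.** **Inputs**
- 8 clinics, 24 patients each: section D.1. 8 × 24 = 192.
- 4 clinics to SMASH: Human Subjects 1.a, on the healthcare team focus groups ("whose 4 practice sites are randomly selected to deliver SMASH"). That leaves 4 for SC, and 4 × 24 = 96 patients per arm.
- 16 recruits per month, months 4 to 15: section D.4. 12 × 16 = 192.
- Intervention in months 5 to 22: section D.4, Table 2.
- 79% below the adherence cut-off on the tray, and 91% acceptance into randomisation: section D.12.

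**Step 1: reproduce the stated chance.** There are C(8,4) = 70 ways to choose the 4 SMASH clinics. A given clinic is among them in C(7,3) = 35. So before the draw a patient's chance of SMASH is 35/70 = 0.5, and the stated figure is right at that moment.

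**Step 2: the chance after the draw.** It is 1 for patients of the 4 SMASH clinics (96 of 192) and 0 for patients of the 4 SC clinics (96 of 192). It is 0.5 for nobody.

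**Step 3: how many patients come after the draw.** In Table 2 recruitment appears to mark the start of screening: a patient recruited in month 15 has one month of tray screening and six of intervention, and 15 + 1 + 6 = 22, the last intervention month. The first patients start intervention in month 5, so a single draw of all eight sites must be made by the start of month 5 at the latest.
- Recruited before that: 1 × 16 = 16.
- Recruited after it: 11 × 16 = 176, and 176/192 = 92%.
- If the sites are drawn before the first call, as the tense in Human Subjects 1.a suggests: 192 of 192.

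This assumes one draw for all eight sites, even accrual, and a call in the same month as recruitment. The 176 here is unrelated to the 176 in the sample size section (D.8).

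**Step 4: how many people undergo the tray month.** 192/(0.79 × 0.91) = 192/0.7189 ≈ 267, of whom about 134 would be at SC clinics. This assumes an even split between arms and ignores failures at the repeat blood pressure check.

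**The case against.** The best defence has three parts.

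**The figure can be right.** Clinics are assigned by chance, and each patient's chance is exactly 0.5 until the draw. Section D.3.b mentions site assignment after the end-of-screening rule, and the sentence in Human Subjects 1.a gives no date relative to the first calls. This stands in part: an early draw is an inference, not a stated fact. But the timetable limits the defence to about one month of recruits if the sites are drawn together. Even for them, the statement describes a draw applied to the eligible patient, which is not the design.

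**The sentence is not the consent form.** It paraphrases a first phone contact. Written consent follows at the screening visit, after risks and benefits are explained and questions answered, and section 2.a says the IRB has approved the consent document. This stands. A reader might infer that patients consent on a false statement, but the form is not among the documents and may describe clinic assignment correctly.

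**No harm to the trial is shown.** A reader might expect disappointed SC patients to withdraw, or patients of one clinic to discover the mismatch by comparing notes. The documents support neither. They give no withdrawal rate tied to the wording. Disappointment at receiving control could arise under an accurate statement too. The two later feasibility trials report retention of 95% and 96%. Human Subjects 1.a tells subjects not to discuss their regimen outside the household. This objection stands in full.

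**Conclusion.** The inconsistency is real, and no section resolves it. The recruitment statement describes individual even allocation after screening, whereas the plan allocates clinics. With one draw of all eight sites, about 176 of 192 enrolled patients (92%), and possibly all 192, are recruited when their chance of SMASH is already 0 or 1.

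A reader might take the problem to affect only half the patients. It affects everyone called after the draw, because a patient certain to receive SMASH is also told something untrue. Half is only the share with no chance of SMASH.

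The conclusion rests on the single-draw reading of section D.3.b and on the timetable in D.4. It covers what candidates are told by phone. It does not establish that written consent is defective, that dropout will differ between arms, or that the treatment comparison is biased.

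**What to change.** 1. State the date of the site draw relative to the first recruitment call, and reconcile D.1, D.3.b and both statements in Human Subjects 1.a.
2. Replace the equal-chance statement with identical wording at every site: clinics, not individuals, are assigned by chance to one of two programmes, and everyone enrolled at a clinic receives the same one. Tell each patient which programme it is only after the baseline evaluation is complete.
3. Check that the consent form says the same.

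The cost is an IRB wording amendment, with no change to design, sample size or analysis. One downside should be accepted openly: once patients know that the whole clinic shares a programme, later recruits may be able to infer their arm from earlier ones.

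Keeping the present wording by assigning each clinic only after its patients have enrolled is not a workable alternative. It conflicts with rolling recruitment over months 4 to 15 and intervention from month 5, and could leave early enrollees waiting for months.

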D.3. Recruitment: Proposed procedures were successful in our SMASH pilot trials.^{22,23,25,26} Practice sites will prepare a list of eligible patients and [name] (project manager) will contact them, explain the study and, if interested, schedule the screening/recruitment visit. As part of **design rigor**, other MUSC staff will conduct the evaluations below using established protocols. They will remain blinded as to patients' group status throughout study (i.e., baseline, 3 and 6 months, and post-trial follow-ups at 12 and 18 months). Subjects who develop any comorbidities over the study period will remain in the trial and all meds will be monitored.

D.3.a. Resting and 24-hr BP screening: After obtaining informed consent, resting BP protocol will be conducted using our established protocol with the previously validated BpTRU device.¹¹⁶ **If SBP ≥ 140 mmHg** from last 2 readings of 10 min protocol, **they will continue with screening:** height, weight and waist/hip ratio will be recorded (BP and anthros protocols in Appx. 5 and 6). Based on their preference, a set of **questionnaires will be given** orally or read on their own (see D.6 Measures; Table 3; copies in Appx. 7-21). They will have the option of using their smart phone, TACHL provided tablet, or paper copy version. They will **then wear** the previously validated¹¹⁷ **SpaceLabs 90207 BP monitor for 24 hrs** using our established protocol.¹¹⁸⁻¹²⁰ Protocol and criteria for acceptable readings, generating 24-hr averages, etc. are in Appx. 22. **Only those with 24hr SBP ≥ 130 mmHg will proceed to the MNA identification phase below.**

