The MUSC IRB has approved the use of SMASH, the various study procedures, and the ICD. The practice site MDs and nurse managers maintain CITI certification. Several Fetter Health Care Network (FHCN) MDs are quite familiar with SMASH, as they jointly participated in the development of the provider portion of the program. They helped design the MD summary report contents and how such a program can best function given the way their FHCN center (and other FQHCs) operate. They will receive training from the PI, [name], project manager, [name], and Co-I, [name], on the rationale for the SMASH efficacy trial and how the programs will operate. The SMASH project manager, [name], will contact potentially eligible patients by phone to gauge their interest. If they express an interest in participating, they will be invited to an initial screening at the FHCN clinic. She will explain the risks and benefits of study participation at the time of their screening visit. Interested participants will have all of their questions answered and will sign a written informed consent document. All participants will be reminded that they are free to contact study personnel or the PI at any time if any questions or concerns arise. They will be provided a copy of the written consent with the SMASH project with contact information for the project manager, the PI, and the MUSC IRB Chair.

b. Protections Against Risks

All the material delivered to the SMASH cohort by smart mobile phone and to the SC cohort either by mobile phone or hard copy mail are hygienic and health promoting and non-invasive with no known adverse physical side effects and present no more than minimal risk to the subject. With exception of standard of care blood draws, the study procedures are non-invasive and present no more than minimal risks to the subject. Subject data will be stored with coded ID numbers and no identifiers will accompany the data files. Confidentiality will be maintained. [name] will keep all records in locked storage areas and on encrypted network storage.

3. Potential Benefits of the Proposed Research to Human Subjects and Others

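### An unblinded project manager recruits patients, with provider assent and no call-order rule, while the clinic's arm can already be known, so selection can differ by arm

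*Combined protocol and SAP*

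**What the plan says.** All references are to the combined protocol and SAP. D.1 randomises clinics and analyses patients: 8 clinics, 24 patients each.

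- **Allocation.** Protection of Human Subjects 1.a: "The practice sites will have been randomly assigned to SMASH or SC". D.3.b, after describing the screening steps and without a date, says that a team member "will randomly assign the 8 sites to either SMASH or" enhanced standard care. Section 1.a also says that patients are told on the first call that "they will have an equal chance of being randomized to either the enhanced health education" arm or SMASH, if found eligible after screening.
- **Timetable (D.4).** Recruitment is 16 per month in months 4-15. Intervention runs in months 5-22.
- **Recruiter.** Under 2.a the project manager "will contact potentially eligible patients by phone to gauge their interest", and "She will explain the risks and benefits of study participation at the time of their screening visit". Section 1.a keeps her out of data collection, "as she will be a phone contact for SMASH subjects and will not be blinded".
- **List.** D.3: "Practice sites will prepare a list of eligible patients". Section 1.a gives this task to the health-centre network's IT department.
- **Provider.** An inclusion criterion (D.2 and 1.a) is the primary care provider's "assent that patient is able to participate". Under D.5.b, SMASH providers receive weekly reports on their patients.
- **Safeguards.** Technicians who evaluate patients are blinded (D.3, 1.a). Entry needs a low possession ratio over 3 months, a low one-month tray score with reminders off, and clinic and 24-hour systolic pressure above threshold, both reconfirmed (D.2, D.3.b, 1.b).

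**The concern.** In a cluster trial, randomising clinics protects the comparison only if the people who list, call, assent to and consent patients do not know the clinic's arm, or have no discretion. Here the caller knows the arm, the provider can learn it, and nothing fixes which listed patients are called or in what order. SMASH clinics could enrol patients who seem more willing or better suited to the program, while control clinics take whoever agrees. The arms would then differ at baseline for reasons unrelated to treatment. Both primary outcomes, BP control and adherence above 0.90, could be affected.

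There is also a plain accuracy problem. Once a clinic has been allocated, its patients no longer have an equal chance of either arm, so what they are told on the first call is not correct for them.

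**Working it through.** **1. The plan's own counts reproduce.** 16 per month x 12 months = 192, and 24 per clinic x 8 = 192. The pool in D.12 is 2,619 x 0.75 x 0.79 x 0.91 = 1,412, against about 1,411 stated.

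**2. How much recruitment can follow allocation.** Intervention starts in month 5, so allocation must exist by then for at least the first clinics. Recruitment months 5-15 number 11 of 12, or 11 x 16 = 176 of 192 patients (92%). Counting only months 6-15 gives 160 of 192 (83%). These are upper figures if clinics start at different times and learn their arm only then.

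**3. How much discretion there is.** 1,411 / 8 = about 176 projected enrollable patients per clinic on average, for 24 places: 24 / 176 = 14%. No section states a call-order rule.

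**4. The conflicting statements side by side.**

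| Item | One place | Another place |
|---|---|---|
| Who prepares the list | Practice sites (D.3) | Network IT department (1.a) |
| When sites are assigned | Already assigned (1.a) | Mentioned after screening, undated (D.3.b) |
| What the patient is told | Equal chance if eligible after screening (1.a) | Clinic is the randomised unit (D.1) |

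**5. Illustrative size.** The documents give no outcome data on people who decline. If a fraction f is lost at a step where the arm may be known, and in one arm only those lost differ from those enrolled by d points, the enrolled group in that arm shifts by f x d. The plan supports several values of f:

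- Final acceptance step only (D.12): 1 - 0.91 = 9% of those reaching it.
- D.1 rates: 1 - 0.90 x 0.93 = 16%.
- D.12 rates with the tray criterion between the two steps: 0.25 + 0.75 x 0.79 x 0.09 = 30%.
- D.12 rates without it: 1 - 0.75 x 0.91 = 32%.

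With d assumed to be 10 to 20 points, the range runs from 0.09 x 10 = 0.9 to 0.3175 x 20 = 6.4 points, or about 1 to 6.

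**6. What such a shift does to the test.** Assume no treatment effect, a control rate of 25-40%, and the D.8 values of 88 per arm and ICC 0.04. The variance inflation is 1 + 21 x 0.04 = 1.84, and the effective size is 88 / 1.84 = 47.8 per arm. A 5-point shift raises the rejection rate of a cluster-adjusted 5% test to about 8%. A 10-point shift, beyond the range in step 5, would give 17-19%.

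**The case against.** The strongest reply is that eligibility is measured. Low possession ratio, low tray score and reconfirmed high pressure remove patients who already adhere well, and both arms must own a smartphone with a data plan. Evaluators are blinded. If the IT list is the one used, sites have less influence on who is considered. Patients in both arms hear the same statement on the first call, so their own refusal at that step is not informed by the arm. All of this stands and limits the bias. None of it governs whom the unblinded manager calls first, how she presents the study, or whom the provider withholds.

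Some stronger readings are tempting but not supported:

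- *Providers are told their arm at orientation.* Section 1.a describes orientation to the study and a guideline refresher. That SMASH providers learn their arm from the weekly reports is an inference from D.5.b.
- *Sites control the list.* D.3 and 1.a conflict, and neither can be taken as settled.
- *D.3.b places allocation after screening.* It gives no date. The timetable overlap carries the argument.
- *Nothing in the analysis can help.* Motivation and competence are measured at baseline (D.6). D.10 includes adjusted logistic regression, longitudinal models with the baseline value, and exploratory models with autonomous motivation. These can partly correct selection on measured factors, but not on unmeasured ones. The first primary comparison in D.10, the Cochran-Mantel-Haenszel test, is for unadjusted differences.

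**Conclusion.** The point holds as a risk of differential selection that the plan does not close; it does not show that bias will occur. It rests on three documented facts: an unblinded recruiter who also leads consent, overlap of recruitment with intervention in up to 11 of 12 months, and no concealment or call-order rule for a pool about seven times the places available (1,411 / 192 = 7.3).

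The size cannot be computed from the documents. The 1 to 6 points depend on an assumed 10-20 point gap confined to one arm, and on which of the plan's participation rates applies. A reader might infer that selection could produce the planned 30-point difference; a shift of this size could not. It would matter if the true effect were much smaller than planned. The conflicts over the list and over allocation timing, and the statement made to patients, need correcting whatever the size of any bias.

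**What to change.** 1. Reconcile D.3 with Protection of Human Subjects 1.a by using only the IT-generated list, in a random call order per clinic fixed before allocation. Add patients who become eligible later by periodic IT refresh, also in random order, and call strictly in that order.
2. Obtain provider assent for listed patients before the site learns its allocation, where feasible. Log every refused assent with its reason.
3. Use a fixed, arm-neutral text for the call and the consent discussion. Do not tell patients their clinic's arm until after the baseline re-confirmation visit.
4. In 1.a, replace the equal-chance statement with one saying that the patient's clinic is assigned by chance.
5. State one allocation date in both D.3.b and 1.a. Report numbers listed, called, assented, screened, eligible and enrolled by clinic and arm. Compare baseline motivation, possession ratio, tray score and BP by arm.

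Calls and consent should not be moved to the blinded BP assessors. Because clinic determines arm, the extra contact could unblind a primary outcome, and the documents do not show that these staff have the capacity: at the D.12 rates, 192 / (0.75 x 0.79 x 0.91) = about 356 calls are needed even before BP screen failures.

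The cost is a protocol and wording amendment, periodic list refreshes, less flexibility in call order and slightly slower recruitment. No extra patients or study procedures are needed. The recruiter stays unblinded, so some risk remains.
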